3.5 Estimated Study Duration

3.5.1 Study Duration for Subjects

The subject enrollment period is planned for approximately 17 months.

The duration of the screening period for each subject will be up to 28 days. The duration of treatment will vary for each subject. Subjects will be treated with talimogene laherparepvec until the subject has achieved a CR, all injectable tumors have disappeared, clinically relevant (resulting in clinical deterioration or requiring change in therapy) disease progression beyond 6 months of treatment, per modified WHO response criteria ([Appendix D](#)), or intolerance of study treatment, whichever occurs first. Subjects will be followed for safety 30 (+ 7) days after the last dose of talimogene laherparepvec and for survival, **adverse events thought by the investigator to be potentially related to talimogene laherparepvec, and use of anti-cancer therapy for melanoma** every 12 weeks (\pm 28 days) for up to approximately 24 months after the last subject is enrolled **in the study**. The estimated average per-subject study duration is approximately 32 months.

After the end of the long term follow up subjects who end the study for any reason other than death or withdrawal of full consent will continue to be followed for survival under an ongoing separate registry protocol (Study 20120139). The registry protocol will also monitor for adverse events thought by the investigator to be potentially related to talimogene laherparepvec and use of anti-cancer therapies for melanoma.

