A subject will be treated with talimogene laherparepvec until the subject has achieved a CR, all injectable tumors have disappeared, clinically significant (resulting in clinical deterioration or requiring change of therapy) disease progression beyond 6 months of treatment, per modified World Health Organization (WHO) response criteria (Appendix D), or intolerance of study treatment, whichever occurs first. Due to the mechanism of action, subjects may experience growth in existing tumors or the appearance of new tumors prior to maximal clinical benefit of talimogene laherparepvec. Therefore, dosing should be continued for at least 6 months from the time of initial dose, provided that the subject has no evidence of clinically significant deterioration of health status requiring discontinuation of treatment with talimogene laherparepvec and is able to tolerate the treatment.

The dose, start date, and lot number of talimogene laherparepvec are to be recorded on the electronic case report form (eCRF).

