If talimogene laherparepvec dosing is delayed by more than 4 weeks from the date of the planned dose (ie, approximately 6 weeks from the previous dose) due to the occurrence of an adverse event that is considered related to talimogene laherparepvec, the subject must be permanently withdrawn from talimogene laherparepvec treatment.

If talimogene laherparepvec dosing is delayed by more than 4 weeks from the date of the planned dose (ie, approximately 6 weeks from the previous dose) for reasons other than treatment-related toxicity, the case must be reviewed by the Amgen medical monitor in conjunction with the investigator to determine if the subject can resume talimogene laherparepvec therapy.

Talimogene laherparepvec is to be permanently discontinued for subjects meeting any of the following criteria:

- The subject, for any reason, requires treatment with another anticancer therapeutic agent for treatment of the study disease (other than the exceptions noted in [Section 6.5](#)). In this case, discontinuation from the treatment occurs immediately upon introduction of the new agent.
- Clinically relevant disease progression beyond 6 months of treatment occurs as defined per the modified WHO response criteria ([Appendix D](#)).
- A grade 2 or greater immune-mediated adverse event (with the exception of vitiligo) or allergic reactions attributed to talimogene laherparepvec that would require a dose delay of greater than 4 weeks from the date of the planned dose (ie, approximately 6 weeks from the previous dose).

Note: immune-mediated glomerulonephritis, vasculitis, and pneumonitis and exacerbation of psoriasis have been observed in subjects receiving talimogene laherparepvec in clinical trials. Most of these subjects had a history of other autoimmune disease and/or prior treatment with agents that offered plausible

alternative etiologies, however, immune-mediated adverse events can potentially involve any organ system.

- Any other talimogene laherparepvec-related non-hematologic or hematologic toxicities grade 3 or greater occur that, in the opinion of the investigator, would require a dose delay of greater than 4 weeks from the date of the planned dose (ie, approximately 6 weeks from the previous dose).
- The subject develops clinical evidence of any systemic herpes infection (such as encephalitis or disseminated infection).

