- ^p Tumor biopsy **from cutaneous, subcutaneous or nodal lesions** for biomarker analysis **should not be collected prior to the subject being enrolled. Tumor biopsy should be collected** (within 5 days prior to **first** talimogene laherparepvec administration) from one lesion at day 1 of week 1 [**Cycle 1**] and, if there are ≥ 2 lesions at baseline and one is left uninjected as described in [Section 6.2.1.1](#), from an uninjected lesion **within 7 days prior to dose** at day 1 of week 6 [**Cycle 3**]. Also **within 7 days after documentation of disease progression followed by treatment discontinuation** from the **available cutaneous, subcutaneous or nodal** lesion responsible for PD **and easily accessible for biopsy with or without ultrasound guidance**. Note: uninjected lesion biopsied at day 1 of week 6 [**Cycle 3**] must be different lesion from the lesion biopsied at day 1 of week 1 [**Cycle 1**].
- ^q Investigator's clinical measurement of cutaneous, subcutaneous, or nodal tumor by caliper at screening, day 1 of week 12 (± 1 week) [**Cycle 6**] and then every 12 weeks (± 1 week), or more frequently if clinically indicated, until clinically relevant disease progression beyond 6 months of treatment (per modified WHO response criteria, [Appendix D](#)) or until the start of a new anticancer therapy. The screening measurement must be done within 28 days prior to enrollment and will be used as baseline. If subject discontinues talimogene laherparepvec for reason other than disease progression or death, clinical tumor measurements are to be performed at safety follow-up visit (if not performed within previous 4 weeks [+ 1 week]) and every 12 weeks (± 1 week) during the long term follow-up period until clinically relevant disease progression beyond 6 months of treatment (per modified WHO response criteria, [Appendix D](#)) or until the start of a new anticancer therapy.

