Disease Progression (PD):	
A > 25% increase in the sum of the products of the perpendicular diameters of all index tumors since baseline, or the unequivocal appearance of a new tumor since the last response assessment time point.
 
There are 2 types of PD defined in this protocol:
 
Non-clinically relevant disease progression (PDn): PD in subjects who do not suffer a decline in performance status and/or in the opinion of the investigator do not require alternative therapy. Subjects showing overall response as PDn will be allowed to continue study treatment.
 
Clinically relevant disease progression (PDr): PD that is associated with a decline in performance status and/or in the opinion of the investigator the subject requires alternative therapy. Subjects with PDr will be allowed to remain on study until 24 weeks of therapy unless, in the opinion of the investigator, other treatment is warranted.

Stable Disease (SD):	Neither sufficient tumor shrinkage of index lesion to qualify for response (PR or CR) nor sufficient tumor increase of index lesion to qualify for PD.
Unable to Evaluate (UE):	Any index lesion present at baseline which was not assessed or was unable to be evaluated leading to an inability to determine the status of that particular tumor for that time point.
Not Done (ND)	Radiographic image or clinical measurement were not performed at this time point to evaluate the index lesions

Table 6. Definition of Nonindex Lesion Tumor Response

Complete Response (CR):	Disappearance of all nonindex lesions.
Incomplete Response/Stable Disease (SD):	Persistence of one or more nonindex tumor(s).
Disease Progression (PD):	Unequivocal progression of one or more nonindex lesions There are 2 types of PD defined in this protocol: Non-clinically relevant disease progression (PDn): PD in subjects who do not suffer a decline in performance status and/or in the opinion of the investigator do not require alternative therapy. Subjects showing PDn as overall response will be allowed to continue study treatment. Clinically relevant disease progression (PDr): PD that is associated with a decline in performance status and/or in the opinion of the investigator the subject requires alternative therapy. Subjects with PDr will be allowed to remain on study until 24 weeks of therapy unless, in the opinion of the investigator, other treatment is warranted.

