Unable to Evaluate (UE):	Any nonindex lesion present at baseline which was not assessed or was unable to be evaluated leading to an inability to determine the status of that particular tumor for that time point.
Not Applicable (NA)	No nonindex lesions were identified at baseline
Not Done (ND)	Radiographic image or clinical measurement were not performed at this time point to evaluate the nonindex lesions

Table 7. Matrix for Determining the Overall Response at Each Assessment Point

Index Lesion Response Including New Lesions	Nonindex Lesion Response	Overall Response
CR	CR	CR
	SD	PR
	PDn	PDn
	PDr	PDr
	NA	CR
	UE/ND	UE
PR	CR/SD	PR
	PDn	PDn
	PDr	PDr
	NA	PR
	UE/ND	UE
SD	CR	SD
	SD	SD
	PDn	PDn
	PDr	PDr
	NA	SD
	UE/ND	UE
	PDn	CR/SD/PDn/NA/UE/ND
PDr		PDr
PDr	Any	PDr
UE/ND	CR/SD/ NA/UE/ND	UE
	PDn	PDn
	PDr	PDr

Subjects with PDn as overall response will be allowed to continue study treatment.

Subjects with PDr will be allowed to remain on study until 24 weeks of therapy unless, in the opinion of the investigator, other treatment is warranted.

CR = complete response; PR = partial response; SD = stable disease; PD = disease progression; PDn = nonclinically disease progression; PDr = clinically relevant disease progression; UE = unable to evaluate; NA = not applicable; ND = not done.

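### Appendix D defines non-clinically relevant progression (PDn) with *and/or*, so a progression with only one component meets both PDn and PDr, and a decline-only progression can be a TTF event or not depending on the label

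*Protocol*

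**What the plan says.** Protocol Appendix D splits disease progression into two types, with the same wording in Table 5 (index lesions) and Table 6 (nonindex lesions):

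- PDn (non-clinically relevant): "PD in subjects who do not suffer a decline in performance status and/or in the opinion of the investigator do not require alternative therapy".
- PDr (clinically relevant): "PD that is associated with a decline in performance status and/or in the opinion of the investigator the subject requires alternative therapy".

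Table 7 combines the index and nonindex labels and gives PDr precedence when the two differ. Its note adds: "Subjects with PDn as overall response will be allowed to continue study treatment". Subjects with PDr may stay until 24 weeks of therapy unless the investigator thinks other treatment is warranted.

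The body text uses an either-component rule. Section 3.5.1 refers to "clinically relevant (resulting in clinical deterioration or requiring change in therapy) disease progression beyond 6 months of treatment". Section 6.2.1.1 has "clinically significant (resulting in clinical deterioration or requiring change of therapy) disease progression beyond 6 months of treatment", and the Synopsis, Section 3.1 and Table 2 footnote t give the same rule. Section 6.2.1.2 lists two relevant grounds for permanent discontinuation: "The subject, for any reason, requires treatment with another anticancer therapeutic agent for treatment of the study disease" (first bullet) and "Clinically relevant disease progression beyond 6 months of treatment occurs as defined per the modified WHO response criteria" (second bullet). Tumour assessments run "until clinically relevant disease progression beyond 6 months of treatment" or until new anticancer therapy (Table 2 footnotes q and r; Section 7.2.2).

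SAP Section 6 counts three kinds of TTF event: (1) PDr; (2) death from any cause; (3) PDn with a requirement for alternative therapy as the reason for ending treatment, or start of new anticancer therapy. Subjects without an event are censored at the last evaluable tumour assessment.

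**The concern.** The two labels are meant to divide progression into relevant and non-relevant. If PDr means either component is present, its complement is that neither is present. The PDn wording instead says that at least one is absent. An investigator facing a progression with a performance-status decline but no need for other therapy, or the reverse, can apply either label and comply with the text.

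The choice matters because the SAP treats the labels differently. PDr is a TTF event by itself; PDn is not. TTF is a secondary efficacy endpoint, so for some subjects its event status and date could rest on which of two satisfied definitions the investigator chose. The label also feeds the second discontinuation bullet in Section 6.2.1.2 and the point at which tumour assessments stop.

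**Working it through.** There is no stated figure to reproduce. The check is a truth table followed by a mapping to the TTF rules.

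**Inputs.** D = decline in performance status; T = investigator considers alternative therapy necessary. From Tables 5 and 6:

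- PDr = D or T
- PDn as written = (not D) or (not T)
- PDn with *and* = (not D) and (not T)

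| D | T | PDr | PDn as written | Both, as written | PDn with *and* | Both, with *and* |
|---|---|---|---|---|---|---|
| no | no | no | yes | no | yes | no |
| no | yes | yes | yes | **yes** | no | no |
| yes | no | yes | yes | **yes** | no | no |
| yes | yes | yes | no | no | no | no |

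As written, 2 of 4 combinations carry both labels. With *and*, the overlap is 0 of 4 and every progression has exactly one label. These are logical cells, not proportions of subjects.

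**Is there a tie-break?** Table 7 settles disagreement between the index label and the nonindex label. It takes each label as given, so it does not help when one progression satisfies both definitions.

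**What was intended?** Section 3.5.1 uses the term *clinically relevant* and says deterioration or a change of therapy is enough. That puts both overlapping cells in PDr. The body text speaks of clinical deterioration and Appendix D of performance status; I treat the second as a form of the first.

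**Effect on TTF, decline only (D yes, T no).** Labelled PDr, it is an event at that assessment under clause 1. Labelled PDn, clause 3 is not met at that point, because there is no requirement for alternative therapy and none has started. The subject becomes an event only on a later PDr, death, or fulfilment of clause 3, and is otherwise censored. For example, a decline-only progression at the week 12 assessment is an event at week 12 as PDr. As PDn, the next scheduled tumour assessment is at 12 + 12 = 24 weeks (±1 week), unless an earlier one is clinically indicated. Both status and date can change.

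**Effect on TTF, therapy only (D no, T yes).** Labelled PDr, it is an event under clause 1. Labelled PDn, it is an event under clause 3 if the requirement is why treatment ended or if new therapy starts. Status differs only if neither holds, for instance in a subject already off treatment who starts nothing new. The visible SAP text does not show how clause 3 events are dated, and text after the TTF definition is redacted, so nothing can be concluded about dates here.

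**The case against.** The strongest reply is that this is a drafting slip the rest of the protocol already resolves. PDn is named as the non-relevant category, Section 3.5.1 says what makes progression relevant, and an investigator would hardly call a progression with a performance-status decline non-relevant. This largely stands as evidence of intent: the documents favour PDr. It does not remove the contradiction, because the PDn definition is the operative text and says otherwise. Nor does the rest of the plan confirm that the categories are exclusive. SAP clause 3 provides for a PDn linked to a need for alternative therapy, and Section 7.2.2 provides for a PDn that led to treatment discontinuation. Either could describe a need arising after the PDn, so neither proves misuse.

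Three stronger readings are tempting, and the documents do not support them.

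- A reader might infer that the PDn label lets a deteriorating subject stay on treatment beyond 6 months. The permission in Table 7 is only a permission. The stopping rules in Section 6.2.1.1 and Table 2 footnote t spell out deterioration or change of therapy inline and apply whatever the label. Where another anticancer agent is needed, the first bullet of Section 6.2.1.2 ends treatment regardless.
- A reader might infer that both overlapping cells distort TTF equally. Clause 3 picks up most therapy-only cases; the clear effect is in the decline-only cell.
- A reader might infer a threat to the primary endpoint. Both labels are progression, so the choice does not directly change ORR.

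**Conclusion.** The definition is wrong as written. PDn and PDr overlap for any progression with exactly one component, contrary to the body text, and Table 7 provides no tie-break for that case. The main consequence is that a decline-only progression is a TTF event at once under one label, but under the other only if a later qualifying event occurs. The label also bears on the second discontinuation bullet in Section 6.2.1.2 and on how long tumour assessments continue.

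The size of the effect is unknown, because the documents give no frequency of one-component progression. The stakes are limited: TTF is a descriptive secondary endpoint in a single-arm study without formal hypothesis testing, and SAP Section 12 anticipates replacing it with PFS. That replacement would not by itself correct the label on which the discontinuation bullet and the assessment schedule rely.

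The conclusion rests on reading *and/or* in its ordinary inclusive sense and on treating performance-status decline as a form of clinical deterioration.

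**What to change.** In both Table 5 and Table 6, define PDn as progression with no decline in performance status **and**, in the investigator's opinion, no need for alternative therapy. Keep PDr as either component. SAP clause 3 can stay; it would then cover a PDn after which a need for alternative therapy arises.

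The cost is one word in each of two tables, but it is a protocol amendment: Section 12.1 requires investigator agreement and IRB/IEC approval, and Section 3.2 plans about 50 sites. Bundle it with the amendment the SAP already anticipates for the change to PFS. The wording change needs no new procedure or data.

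Optionally, for progressions already recorded, run one TTF sensitivity analysis that counts a PDn as an event if ECOG at that assessment is worse than baseline (per SAP Section 6, the latest value on or before the first dosing date). Report it as approximate, not as an upper bound. It can overcount, by including declines unrelated to the progression. It can also undercount: ECOG is scheduled every 12 weeks, so an unscheduled tumour assessment may have no score. Appendix D also gives no reference point for a decline, so a subject going from ECOG 1 at baseline to 0 and back to 1 would be missed if decline is judged from the previous visit.

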Appendix E. Eastern Cooperative Oncology Group Performance Status Scale

Grade	Description
0	Fully active, able to carry on all predisease performance without restriction.
1	Restricted in physically strenuous activity but ambulatory and able to carry out work of a light or sedentary nature, ie, light housework or office work.
2	Ambulatory and capable of all self-care but unable to carry out any work activities. Up and about > 50% of waking hours.
3	Capable of only limited self-care, confined to a bed or chair > 50% of waking hours.
4	Completely disabled. Cannot carry on any self-care. Totally confined to bed or chair.
5	Dead

Amendment 1

Protocol Title: A Phase 2, Multicenter, Open-label, Single-arm Trial to Evaluate the Correlation Between Objective Response Rate and Baseline Intratumoral CD8+ Cell Density in Subjects With Unresected Stage IIIB to IVM1c Melanoma Treated with Talimogene Laherparepvec

Talimogene Laherparepvec
Amgen Protocol Number (Talimogene Laherparepvec) 20120325

Amendment 1 Date: 31 August 2015
Superseding Date: 21 September 2015

This document summarizes the changes made to the protocol in both Amendment 1 and the superseding version.

Rationale:

- Removed [Inclusion Criterion 105](#) to allow subjects to join the study after having received first-line therapy.
- Removed exclusion of subjects receiving any non-oncology vaccine therapies used for the prevention of infectious disease within 28 days prior to enrollment and during treatment period ([Exclusion criterion 210](#)).
- Clarified that if no viable cells were found following surgery, the response definition will be complete response (CR).
- Added testing for herpes simplex virus type 2 (HSV-2) within 3 days prior to dose at day 1 of week 1 [Cycle 1], week 6 [Cycle 3], and week 12 [Cycle 6].
- Increased the window to 5 days for tumor biopsy for biomarker analysis for the Week 1 biopsy, 7 days for the Week 6 biopsy, and to 7 days after documentation of disease progression at PD.
- Added assessment of Eastern Cooperative Oncology Group (ECOG) performance status every 3 months during treatment period.
- Revised photography assessments in the schedule of assessments to remove requirement at screening, update cycles, and removed the word “measurable.”
- In Schedule of Assessments, clarified that the week 1 biopsy should not be collected prior to the subject being enrolled.
- Removed word “uninjected” from the correlation between changes in intratumoral CD8+ cell density during treatment and objective response rate in the study endpoints.
- Revised the number of planned sites to be 50.
- Added exclusion criterion to avoid potential viral transmission during sexual contact.
- Specified how lesions that separate or merging are to be assessed.

- Added an interim analysis.
- Added reporting of treatment related adverse events during the long-term follow-up.
- Added addition of anti-cancer therapy for melanoma during long term period follow-up.
- In [Table 5](#): Definition of Index Lesion Tumor Response Including New Lesions, removed the following text from the definition of partial response, “Any residual cutaneous or subcutaneous index or new lesions that must be tumor free for the subject to meet the criteria for partial response (PR) must be documented as such by representative biopsy”.
- Updated text throughout document to specify cycle number corresponding to study week.
- Implemented minor administrative and formatting changes.
- Added references in [Section 2.2](#) and in the reference list.
- Added ECOG and physical examination during treatment period and follow-up period.
- Defined the final analysis after 24 months from LSE rather than keeping it open ended.
- Clarified that unless patient dies or withdraws full consent after they have completed the LTFU portion of the study they will then be transferred to the registry protocol where they will continue to be followed up, until death or full consent withdraw.

Description of Changes:

[Section: Global](#)

Replace:

5 December 2014

With:

21 September 2015

[Section: Synopsis, Secondary Objective\(s\)](#)

Bullet 2

Replace:

to explore the correlation between changes in intratumoral CD8+ cell density during treatment (in injected and uninjected lesions) and ORR, DRR, DOR, and changes in tumor burden

With:

to explore the correlation between changes in intratumoral CD8+ cell density during treatment and ORR, DRR, DOR, and changes in tumor burden

[Section: Synopsis, Secondary Endpoints](#)

Bullet 1

Replace:

correlation between changes in intratumoral CD8+ cell density during treatment (in injected and uninjected lesions) and ORR, DRR, DOR, and changes in tumor burden

With:

correlation between changes in intratumoral CD8+ cell density during treatment and ORR, DRR, DOR, and changes in tumor burden

[Section: Synopsis, Study Design](#)

Paragraph 3

Replace:

Subjects will be followed for safety 30 (+ 7) days after the last dose of talimogene laherparepvec and for survival every 12 weeks (\pm 28 days) for up to approximately

24 months after the last subject is enrolled. Thereafter, subjects will be followed under an ongoing separate registry protocol (Study 20120139) for the long-term survival follow-up of subjects treated with talimogene laherparepvec. The registry protocol will also monitor for late and long-term adverse events thought to be potentially related to talimogene laherparepvec.

With:

Subjects will be followed for safety 30 (+ 7) days after the last dose of talimogene laherparepvec and for survival every 12 weeks (\pm 28 days) for up to approximately 24 months after the last subject is enrolled **in the study**. Thereafter, subjects will be followed under an ongoing separate registry protocol (Study 20120139) for the long-term survival follow-up of subjects treated with talimogene laherparepvec. The registry protocol will also monitor for late and long-term adverse events thought to be potentially related to talimogene laherparepvec **and use of anti-cancer therapy for melanoma**.

[Section: Synopsis, Study Design](#)

Paragraph 4

Replace:

Blood and tumor tissue samples will be collected at timepoints outlined in the Schedule of Assessments (Table 2). Tumor biopsies will be performed on an uninjected lesion on day 1 of week 1, on a different uninjected lesion at week 6 (if available), and at disease progression (PDn or PDr beyond 6 months of treatment) on the lesion responsible for PD as outlined in Section 7.2.2. Samples will be analyzed to explore if intratumoral CD8+ cell density at baseline and its change during treatment is correlated with the objective response rate in subjects with unresected stage IIIB-IVM1c melanoma treated with talimogene laherparepvec.

With:

Blood and tumor tissue samples will be collected at timepoints outlined in the Schedule of Assessments (Table 2). Tumor biopsies (**taken from accessible cutaneous, subcutaneous or nodal lesions**) will be performed on an uninjected lesion on day 1 of week 1, on a different uninjected lesion at week 6 (if available), and at disease progression **that results in treatment discontinuation from** the lesion responsible for **progression** as outlined in Section 7.2.2. Samples will be analyzed to explore if intratumoral CD8+ cell density at baseline and its change during treatment is correlated

with the objective response rate in subjects with unresected stage IIIB-IVM1c melanoma treated with talimogene laherparepvec.

[Section: Synopsis, Key Inclusion Criteria](#)

Replace:

Male or female ≥ 18 years of age with histologically confirmed diagnosis of stage IIIB to IVM1c melanoma for whom surgery is not recommended. Subject must be treatment naïve with no prior systemic anticancer treatment for melanoma. Subject must have measurable disease and must be a candidate for intralesional therapy with at least 1 injectable cutaneous, subcutaneous, or nodal melanoma lesion (≥ 10 mm in longest diameter) or with multiple injectable lesions that in aggregate have a longest diameter of ≥ 10 mm. Also, subject must have an Eastern Cooperative Oncology Group (ECOG) performance status of 0 or 1 and must have a serum lactate dehydrogenase (LDH) ≤ 1.5 X upper limit of normal and adequate hematologic, hepatic, and renal organ function.

With:

Male or female ≥ 18 years of age with histologically confirmed diagnosis of stage IIIB to IVM1c melanoma for whom surgery is not recommended. Subject **who is** treatment naïve **or had received prior treatment** for melanoma. Subject must have measurable disease and must be a candidate for intralesional therapy with at least 1 injectable cutaneous, subcutaneous, or nodal melanoma lesion (≥ 10 mm in longest diameter) or with multiple injectable lesions that in aggregate have a longest diameter of ≥ 10 mm. Also, subject must have an Eastern Cooperative Oncology Group (ECOG) performance status of 0 or 1 and must have a serum lactate dehydrogenase (LDH) ≤ 1.5 X upper limit of normal and adequate hematologic, hepatic, and renal organ function.

[Section: Synopsis, Key Exclusion Criteria](#)

Replace:

Subject must not have clinically active cerebral metastases, greater than 3 visceral metastases (this does not include lung or nodal metastases associated with visceral organs), or any bone metastases, primary ocular or mucosal melanoma, or history or evidence of symptomatic autoimmune pneumonitis, glomerulonephritis, vasculitis, or other symptomatic autoimmune disease. Subject must not have evidence of clinically significant immunosuppression or active herpetic skin lesions or prior complications of

HSV-1 infection (eg, herpetic keratitis or encephalitis) and must not require intermittent or chronic systemic treatment with an antiherpetic drug (eg, acyclovir), other than intermittent topical use. Subjects known to have acute or chronic active hepatitis B, hepatitis C, or human immunodeficiency virus infection will also be excluded. Subjects must not have any nononcology vaccine therapies used for the prevention of infectious disease within 28 days prior to enrollment and must not have been treated previously with talimogene laherparepvec.

With:

Subject must not have clinically active cerebral metastases, greater than 3 visceral metastases (this does not include lung or nodal metastases associated with visceral organs), or any bone metastases, primary ocular or mucosal melanoma, history or evidence of symptomatic autoimmune **disease (such as** pneumonitis, glomerulonephritis, vasculitis, or other) **or history of autoimmune disease that required systemic treatment (ie, use of corticosteroids, immunosuppressive drugs or biological agents used for treatment of autoimmune diseases) in past 2 months prior to enrollment. Replacement therapy (eg, thyroxine for hypothyroidism, insulin for diabetes mellitus) is not considered a form of systemic treatment for autoimmune disease.** Subject must not have evidence of clinically significant immunosuppression or active herpetic skin lesions or prior complications of HSV-1 infection (eg, herpetic keratitis or encephalitis) and must not require intermittent or chronic systemic treatment with an antiherpetic drug (eg, acyclovir), other than intermittent topical use. Subjects known to have acute or chronic active hepatitis B, hepatitis C, or human immunodeficiency virus infection will also be excluded. Subjects must not have been treated previously with talimogene laherparepvec.

[Section: Synopsis, Screening](#)

Bullet 8

Delete:

~~photographs of visible cutaneous and subcutaneous tumor lesions (select sites only)~~

[Section: Synopsis, Treatment](#)

Bullet 2

Add:

physical examination

[Section: Synopsis, Treatment](#)

Bullet 3

Add:

ECOG Performance Status assessment

[Section: Synopsis, Treatment](#)

Bullet 6, subbullet 2

Replace:

blood samples for herpes simplex virus (HSV-1) antibody serostatus

With:

blood samples for herpes simplex virus (HSV) serostatus

[Section: Synopsis, Treatment](#)

Bullet 8

Replace:

photographs of visible cutaneous and subcutaneous tumor lesions (select sites only)

With:

photographs of **all** visible cutaneous and subcutaneous tumor lesions (select sites only)
always within 3 days of the treatment visit starting from the first treatment visit

[Section: Synopsis, Treatment](#)

Bullet 10

Replace:

administration of talimogene laherparepvec at day 1 of each cycle

With:

administration of talimogene laherparepvec at day 1 of each **treatment** cycle

[Section: Synopsis, Long-term Follow-up/End of Study](#)

Paragraph 1

Replace:

All subjects who permanently discontinue talimogene laherparepvec for any reason other than withdrawal of full consent or death will be contacted by telephone or clinic visit to assess survival every 12 weeks (\pm 28 days) following the safety follow-up visit until death, subject withdraws full consent, or up to 24 months after the last subject is enrolled.

With:

All subjects who permanently discontinue talimogene laherparepvec for any reason other than withdrawal of full consent or death will be contacted by telephone or clinic visit to assess survival, **adverse events thought by the investigator to be potentially related to talimogene laherparepvec, and use of anti-cancer therapies for melanoma** every 12 weeks (\pm 28 days) following the safety follow-up visit until death, subject withdraws full consent, or up to 24 months after the last subject is enrolled **in the study**.

[Section: Synopsis, Long-term Follow-up/End of Study](#)

Paragraph 2

Replace:

If subject has discontinued talimogene laherparepvec for reason other than disease progression or death, radiographic tumor imaging, clinical tumor assessments, and tumor response assessments will be performed until documented disease progression beyond 6 months of treatment, per modified WHO response criteria (Appendix D), or until the start of a new anticancer therapy.

With:

If subject has discontinued talimogene laherparepvec for reason other than disease progression or death, radiographic tumor imaging, clinical tumor assessments, **ECOG Performance Status assessment, assessment of swabs of lesions of suspected**

herpetic origin by qPCR for talimogene laherparepvec DNA, and tumor response assessments will be performed until documented disease progression beyond 6 months of treatment, per modified WHO response criteria (Appendix D), or until the start of a new anticancer therapy **or end of study, whichever the earliest**.

[Section: Synopsis, Long-term Follow-up/End of Study](#)

Paragraph 3

Replace:

After the long term follow-up period of this study has ended, subjects who end the study for any reason other than death or withdrawal of full consent will be followed for survival under an ongoing separate registry protocol (Study 20120139) that is in place for the long-term follow-up of all subjects treated with talimogene laherparepvec in clinical trials. The registry protocol will also monitor for late and long-term adverse events thought to be potentially related to talimogene laherparepvec.

With:

After the long term follow-up period of this study has ended, subjects who end the study for any reason other than death or withdrawal of full consent will be followed for survival under an ongoing separate registry protocol (Study 20120139) that is in place for the long-term follow-up of all subjects treated with talimogene laherparepvec in clinical trials. The registry protocol will also monitor for late and long-term adverse events thought to be potentially related to talimogene laherparepvec **and use of anti-cancer therapies for melanoma**.

[Section: Synopsis, Statistical Consideration](#)

Paragraph 2

Replace:

The main goals of the primary analysis are to evaluate the correlation between baseline intratumoral CD8+ cell density and ORR,DRR,DOR, and changes in tumor burden, in addition to the correlation between changes in CD8+ cell density during treatment (in injected and uninjected lesions) and ORR,DRR,DOR, and changes in tumor burden. The timing of the primary analysis will be when all subjects have had the opportunity to complete 12 months of treatment with talimogene laherparepvec. The final analysis will

occur when the last subject discontinues the study treatment and has had the opportunity to complete the long term follow-up.

With:

The main goals of the primary analysis are to evaluate the correlation between baseline intratumoral CD8+ cell density and ORR, DRR, DOR, and changes in tumor burden, in addition to the correlation between changes in **intratumoral** CD8+ cell density during treatment and ORR, DRR, DOR, and changes in tumor burden. The timing of the primary analysis will be when all subjects have had the opportunity to complete 12 months of treatment with talimogene laherparepvec. The final analysis will occur when the last subject discontinues the study treatment and has had the opportunity to complete the long term follow-up.

[Section: Synopsis, Statistical Consideration](#)

Paragraph 3

Add:

An interim analysis to evaluate the study objectives will be conducted on approximately the first 50 subjects who received at least 1 dose of talimogene laherparepvec, with the biomarker recorded at baseline, and have had the opportunity to be in the study (treatment or follow-up) for 6 months.

[Section: Synopsis, Statistical Consideration](#)

Paragraph 4

Replace:

The final analysis will occur when the last subject discontinues the study treatment and has had the opportunity to complete the long term follow-up.

With:

The final analysis will occur **either 24 months after the last subject has been enrolled or** when the last subject discontinues the study treatment and has had the opportunity to complete the **safety** follow-up, **whichever is later**.

Section: Study Glossary

Delete:

AE(s)	adverse event(s)
------------------	-----------------------------

Section: Study Glossary

Add:

HLA	human leukocyte antigen
------------	--------------------------------

Section: 1.2 Secondary

Bullet 2

Replace:

to explore the correlation between changes in intratumoral CD8+ cell density during treatment (in injected and uninjected lesions) and ORR, DRR, DOR, and changes in tumor burden

With:

to explore the correlation between changes in intratumoral CD8+ cell density during treatment and ORR, DRR, DOR, and changes in tumor burden

Section: 2.1 Melanoma

Paragraph 1, sentence 1

Replace:

Cutaneous melanoma is the fifth most common cancer in men and the seventh most common cancer in women in the United States of America (USA), with an estimated 76,100 new cases and 9,710 deaths expected in 2014 (Siegel et al, 2014).

With:

Cutaneous melanoma is the fifth most common cancer in men and the seventh most common cancer in women in the United States of America (USA), with an estimated **73,870** new cases and **9,940** deaths expected in **2015** (Siegel et al, 2015).

Section: 2.1 Melanoma

Paragraph 3, sentence 3

Delete:

~~For example, dacarbazine or temozolomide achieved a 7% to 12% objective response rate (ORR), but an objective response did not appear to be associated with a prolongation in overall survival~~

Section: 2.1 Melanoma

Paragraph 4, sentence 1

Replace:

